16.5 Safety Analyses

Safety endpoints include all adverse events (CTCAE 5), laboratory safety assessments, and physical examination findings.

16.6 Interim Analysis

An interim analysis for efficacy, futility, and potential sample size re-estimation will be conducted by an independent data monitoring committee (IDMC) when 40 PFS events have been achieved (60% information fraction). Based on the Lan-DeMets method for group sequential trials using O'Brien-Fleming boundaries (Reboussin, DeMets et al. 2000), the levels of significance for the interim and final analyses are alpha=0.00762 and alpha=0.0476, respectively.

Based on the results of the interim analysis, the IDMC will make one of the following four recommendations to the sponsor:

- Terminate the study for efficacy (p<0.00762 at the interim analysis);
- Continue the study as planned;
- Increase the sample size to 120 events;
- Terminate the study for futility.

Provided that the IDMC does not recommend terminating the study early for efficacy, the conditional power of the planned final analysis at 67 events will be computed using the methodology of (Jennison and Turnbull 2000) under the assumption that the observed hazard ratio at the interim analysis represents the true effect. In terms of the HR observed at the interim analysis, these rules can be translated (approximately) as follows:

- If the HR is less than 0.43, terminate for efficacy
- If the HR is in the range from 0.43 to 0.51, continue as planned.
- If the HR is in the range from 0.51 to 0.61 (i.e., conditional power in the range from 50% to 80%), increase the sample size to 120 events.
- If the HR is greater than 0.61 (i.e., conditional power less than 50%), terminate for futility.

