16.0 STATISTICAL CONSIDERATIONS

16.1 Sample Size Justification

This is an open label randomized controlled Phase III clinical trial. Information concerning the predicted survival of the control group is limited, based on rarity of disease and few published reports. However expert advisors in the EWS field estimate a conservative one-year survival rate of 25% in the chemotherapy control group. The one-year survival rate of 60% in the Vigil treated group is estimated from EWS patients treated on the Vigil phase 1 protocol. These estimates correspond to a hazard ratio (HR) of 0.383 favoring Vigil over control.

Assuming 1:1 randomization and the use of a two-sided log rank test at the alpha=0.0476 level of significance, 67 events will provide 90% power to detect an PFS HR of 0.45. Assuming a Group B (control group) median PFS of 6 months, a one-year accrual period, and a six-month follow-up period after randomization of the last subject, it is estimated that the total sample size (number of subjects) required to achieve 67 events is 114 (57 patients in each arm).

An unblinded interim analysis will be conducted by an independent data monitoring committee (IDMC) when 40 PFS events have occurred. Based on the results of this interim analysis, the planned sample size may be increased to 120 events. If the sample size is increased to 120 events, then the study will have approximately 90% power to detect a true HR of 0.55. Note that if the sample size is increased to 120 events, then the accrual period will be extended to 24 months, with a 6-month follow-up period after randomization of the last patient. Under these assumptions, it is estimated that approximately 164 patients will need to be randomized in order to achieve 120 events. Section 16.6 provides further details.

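### The interim HR cut of 0.51 is paired with 80% conditional power but gives 88.9% under the plan's own definition, so interim HRs of 0.51 to 0.54 point to both 120 and 67 events

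*Protocol*

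**What the plan says.** Protocol 16.6, repeated in the Synopsis and in SAP 8.3, places an unblinded look at 40 PFS events. Unless the trial stops for efficacy, "the conditional power of the planned final analysis at 67 events will be computed", with the observed interim HR treated as the true effect. The text then says "In terms of the HR observed at the interim analysis, these rules can be translated (approximately) as follows", and four zones follow:

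- HR below 0.43: stop for efficacy.
- "If the HR is in the range from 0.43 to 0.51, continue as planned". No conditional power is attached to this zone.
- "If the HR is in the range from 0.51 to 0.61 (i.e., conditional power in the range from 50% to 80" (per cent): increase to 120 events.
- HR above 0.61, equated with conditional power under 50%: stop for futility.

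The percentages appear only in brackets inside the HR bullets. No conditional-power rule is written out separately, and no sentence says which scale governs. Protocol 16.1 gives the cost of enlarging: accrual is extended from 12 to 24 months and "it is estimated that approximately 164 patients will need to be randomized in order to achieve 120 events", against 114 patients for 67 events.

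**The concern.** The third bullet makes 0.51 the HR at which conditional power equals 80%. The plan fixes every input to that calculation, so the pairing can be checked.

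If the two numbers do not correspond, there is a range of interim results for which the bullet and its own bracket disagree. The HR says enlarge to 120 events. The conditional power lies above the bracketed 50% to 80% range and so, from the order of the zones, implies continuing to 67 events. Neither action stops the trial, but they exclude each other, and the IDMC would have to choose between them with unblinded results in hand.

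**Working it through.** **Inputs, all from Protocol 16.1 and 16.6 (same in SAP 7.0 and 8.3).** 1:1 randomisation; two-sided log-rank test at 0.0476, critical value 1.981; interim at 40 events, final at 67, so t = 40/67 = 0.597; interim alpha 0.00762, critical value 2.668; design HR 0.45 with 90% power.

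**Step 1: reproduce the plan's own figures** on the log-HR (Schoenfeld) scale.

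- Events for HR 0.45: 4(1.981 + 1.282)²/(ln 0.45)² rounds up to 67. The same formula for HR 0.55 gives 120.
- Lan-DeMets O'Brien-Fleming spending at t = 0.60 gives 0.007616 at the interim and 0.04759 at the final. The plan has 0.00762 and 0.0476.
- Efficacy cut: exp(−2 × 2.668/√40) = 0.430. The plan has 0.43.

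**Step 2: conditional power as the plan defines it.**

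Z1 = −ln(HR) × √40/2, and CP = Φ((Z1/√t − 1.981)/√(1 − t)).

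At HR 0.51: Z1 = 0.673 × 3.162 = 2.129; Z1/√t = 2.756; (2.756 − 1.981)/0.635 = 1.22; CP = 88.9%.

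| Interim HR | Conditional power |
|---|---|
| 0.51 | 88.9% |
| 0.52 | 86.3% |
| 0.53 | 83.5% |
| 0.54 | 80.3% |
| 0.61 | 52.6% |
| 0.62 | 48.5% |

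**Step 3: solve for the cuts.** Since Z1/√t = −ln(HR) × √67/2:

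- CP 80%: −ln(HR) = (1.981 + 0.842 × 0.635)/4.093 = 0.615, so HR = 0.541.
- CP 50%: −ln(HR) = 1.981/4.093 = 0.484, so HR = 0.616.

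**Step 4: other readings.**

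| Reading | At HR 0.51 | 80% falls at HR |
|---|---|---|
| t = 0.60 | 88.8% | 0.540 |
| Critical value 1.96 | 89.5% | 0.544 |
| Freedman form of Z | 85.6% | 0.530 |
| Freedman Z, Schoenfeld drift | 87.0% | 0.535 |

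The Freedman form also fails to reproduce the plan's 67 events (it gives 74) or the 0.43 cut. Values near 80% at HR 0.51 come only from quantities the plan does not define: unconditional power of a 67-event trial (78.1%) and flat-prior predictive power (82.7%, or 79.4% with a Freedman Z).

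**Step 5: how often it matters.** Interim ln(HR) is taken as normal with SD 2/√40 = 0.316. The last two columns are the chance of a significant final result for a trial whose interim HR falls in the band, by simulation of the log-rank score process, with critical value 1.981 at either event count.

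| True HR | Interim HR in 0.51–0.541 | In written increase zone 0.51–0.61 | Success in band, 67 events | Success in band, 120 events |
|---|---|---|---|---|
| 0.45 | 6.6% | 17.8% | 92% | 99.5% |
| 0.50 | 7.3% | 21.0% | 88% | 98% |
| 0.55 | 7.3% | 22.3% | 82% | 95% |
| 0.60 | 6.8% | 21.7% | 75% | 90% |

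**Step 6: effect over all trials**, with recommendations followed, including the futility stop. Power at true HR 0.45, 0.50 and 0.55 is 82.4%, 71.8% and 59.7% as written, and 82.7%, 72.0% and 59.8% with cuts at 0.541 and 0.616. One-sided type I error is about 1.4% and 1.5% respectively.

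**The case against.** The strongest defence is that the HR bullets are the only rules with actions attached and that they cover every HR. Read literally, an interim HR of 0.52 means 120 events. The opposite answer needs a rule that conditional power above 80% means continue, and that rule is nowhere written. This is correct, and the conflict is by implication. But the plan tells the IDMC to compute conditional power and presents the HR cuts as a translation of rules on that scale. A committee that does so finds 86% at HR 0.52, outside the range the bullet gives for enlarging.

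A second point is that the translation is expressly approximate, and on the HR scale the gap is only 0.03, or ln(0.541/0.51) = 0.059, about 0.19 of the interim standard error. Yet the other two cuts agree to within about 0.01 in HR, and this one misses by 9 points of conditional power. Rounding does not produce that.

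Third, the overall effect is small and no false claim becomes easier. That stands, and it limits the weight of the point. Protocol 11.7 also provides for a committee charter. It is not among the documents, so it cannot be assumed either to settle the matter or to leave it open.

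**Conclusion.** The concern holds. Under the plan's own definition HR 0.51 corresponds to conditional power of 88.9%, and 80% falls at HR 0.541. The upper end of the disputed band moves between 0.530 and 0.544 with the approximation used, but no version that fits the stated definition gives 80% at 0.51.

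About 7% of trials would land in the band at true HRs of 0.45 to 0.60, roughly a third of those in the written increase zone. For such a trial the choice between 67 and 120 events changes the chance of success by about 8 to 15 points. Averaged over all trials, power changes by about 1 point or less.

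The documents do not show whether 0.51 or 80% was intended. Unconditional or predictive power may be where 0.51 came from, but nothing confirms it. The case for correction is that an unblinded sample-size rule must give one answer for each interim result, and this cannot be repaired cleanly once the results are known. The figures assume the log-HR scale, a critical value of 1.981 at both event counts, and recommendations that are followed.

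**What to change.** Before the interim analysis, state in the Synopsis, Protocol 16.6, SAP 8.3 and the IDMC charter which scale governs, and align the other to it. Either option works:

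- **Conditional power governs.** Write out that, short of the efficacy boundary, 80% or more means continue to 67 events, 50% to below 80% means increase to 120, and below 50% means futility. Change the HR translation from 0.51 to 0.54 (exact 0.541). The 0.61 may stay as an approximation, but 0.616 is cleaner: between 0.61 and 0.616 the scales otherwise differ between enlarging and futility, and only the statement that conditional power governs settles it.
- **The HR cuts 0.51 and 0.61 govern.** Restate the increase zone as conditional power of about 53% to 89%, and the futility zone as below about 53%, so that no value is unassigned.

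The cost is a text edit in three places plus the charter. Power at true HR 0.45 stays at 82.4% under the second option. Under the first it is 82.7% with cuts 0.541 and 0.616, or 81.9% if 0.61 is applied as the futility cut. With 0.541 and 0.616 the share of trials enlarged at true HR 0.45 falls from 17.8% to 12.0%.

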Autologous Vigil will be supplied by Gradalis, Inc. Irinotecan will be supplied by Clinigen. Temozolomide will be ordered per standard institutional practice.

Group A

- (i) oral temozolomide 100 mg/m² daily (Days 1 5, total dose 500 mg/m²/cycle),
- (ii) oral irinotecan 50 mg/m² daily (Days 1 5, total dose 250mg/m²/cycle), and
- (iii) Vigil 1.0 x 10⁶ cells/injection or cells/injection, intradermally on Day 15.

or

Group B

- (i) oral temozolomide 100 mg/m² daily (Days 1 5, total dose 500 mg/m²/cycle), and
- (ii) oral irinotecan 50 mg/m² daily (Days 1 5, total dose 250mg/m²/cycle).

One cycle equals 21 days.

Duration:

Subjects may receive repeat cycles of treatment until disease progression, unacceptable toxicity, withdrawal of consent or other criterion is met for discontinuation from study. Subjects randomized to Group A, Vigil will receive up to 12 doses depending upon the quantity of Vigil manufactured from the surgical specimen. Within 6 weeks of second relapse or progression, subjects randomized to Group B, will be allowed to cross-over (see Section 10.0) to receive single agent Vigil every 21 days. Subjects who cross-over may receive up to 12 doses of Vigil depending upon the quantity of Vigil manufactured. Cross-over must occur within 2 years of End of Treatment assessments of Group B enrollment. For subjects crossing over, no alternative therapies will be given between End of Treatment and cross-over.

Efficacy Assessments:

- Progression Free Survival (PFS)
- Objective Response Rate (ORR) (RECIST 1.1)
- Overall survival (OS)

Safety Assessments:

- Laboratory assessments
- Physical examination, performance status, height, weight, temperature, blood pressure, and pulse
- Toxicity: CTCAE v 5.0

Exploratory Assessments:

Circulating EWS FLI1 DNA detection and intratumoral immune function analysis including, but not limited to IFNγ-ELISPOT analysis.

Evaluation of baseline tumor microenvironment including, but not limited to immunohistochemical evaluation of tumor PD-L1 expression and tumor infiltrating lymphocyte (TIL) populations.

Statistical Considerations:

The planned sample size of 114 randomized subjects is based on the following assumptions for the PFS endpoint:

- 1:1 randomization;
- Accrual period of 12 months;
- Follow-up period of 6 months;
- Assumed control group median PFS of 6 months from randomization;
- Two-sided test at the alpha=0.0476 level of significance;
- Power 90%;
- Assumed hazard ratio (HR) of 0.45

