11.7 Data Safety Monitoring Board

An independent data monitoring committee (IDMC) or Data Safety Monitoring Board (DSMB) will be established for this trial. Membership will include physicians with appropriate areas of expertise in the therapeutic areas of most interest. A charter will be developed to document their operational methods and timing of safety reviews.

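### The stated 90% power at PFS HR 0.45 ignores the futility stop; with the interim rules followed as written the design has about 82%, and whether the futility rule binds is not stated

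*Protocol*

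**What the plan says.** Protocol 16.1, repeated in SAP 7.0, says that "67 events will provide 90% power to detect an PFS HR of 0.45", using a two-sided log-rank test at 0.0476 with 1:1 allocation. The Synopsis (Statistical Considerations) introduces its list, which includes 90% power and a hazard ratio of 0.45, with "The planned sample size of 114 randomized subjects is based on the following assumptions for the PFS endpoint".

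Protocol 16.6, the Synopsis and SAP 8.3 set one interim analysis at 40 PFS events with four outcomes:

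- stop for efficacy at p<0.00762 (hazard ratio below 0.43);
- continue to 67 events for a hazard ratio of 0.43 to 0.51;
- increase to 120 events for 0.51 to 0.61;
- otherwise: "If the HR is greater than 0.61 (i.e., conditional power less than 50%), terminate for futility".

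For the enlarged trial, Protocol 16.1 adds: "If the sample size is increased to 120 events, then the study will have approximately 90% power to detect a true HR of 0.55".

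On the status of these outcomes, 16.6 says that "the IDMC will make one of the following four recommendations to the sponsor". Protocol 11.7 says of the committee: "A charter will be developed to document their operational methods and timing of safety reviews". Neither document describes the futility rule as binding or non-binding, and neither gives the power of the design with all the interim rules applied.

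**The concern.** A futility stop ends the trial without rejection, so it can only lower power. Here the cut is demanding. The planning hazard ratio is 0.45, the cut is 0.61, and with only 40 events the interim estimate is imprecise. If the chance of crossing the cut under the planned effect is more than 10%, the design cannot have 90% power, whatever happens later.

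The 90% justifies the 67 events and 114 subjects. A sponsor, a data monitoring committee or an ethics board reading the Synopsis would take it as the chance that this trial succeeds if the treatment works as assumed. If the true figure is lower, the risk of missing the planned effect is understated. The committee would then reach the interim analysis without knowing what its futility rule costs.

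**Working it through.** **Inputs.** From Protocol 16.1 and 16.6: 1:1 allocation; interim at 40 events; finals at 67 or 120 events; two-sided levels 0.00762 (interim) and 0.0476 (final), giving critical values 2.668 and 1.981; interim hazard-ratio cuts 0.43, 0.51 and 0.61; planned hazard ratio 0.45. The log-rank Z at d events is taken as normal with mean −ln(HR)·√d/2 and independent increments, so the log hazard ratio at 40 events has standard error 2/√40 = 0.316.

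**Step 1: reproduce the plan's figures.**
- Events needed: 4(1.981 + 1.282)² / (ln 0.45)² = 66.8, i.e. 67.
- Power at 67 events, HR 0.45: Φ(0.7985·√67/2 − 1.981) = Φ(1.287) = 90.1%.
- Adding the 40-event efficacy look only: 90.2%.
- Power of a fixed 120-event test, HR 0.55: Φ(0.5978·√120/2 − 1.981) = 90.2%.

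Both stated powers reproduce, and both are powers without the futility rule.

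**Step 2: chance of a futility stop at true HR 0.45.**
1 − Φ((ln 0.61 − ln 0.45)/0.316) = 1 − Φ(0.962) = 16.8%.
This alone exceeds the 10% type II error implied by 90% power.

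**Step 3: power with all four rules, true HR 0.45.** For each interim zone, the chance of final rejection given the interim Z is integrated over that zone.

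| Interim outcome | Probability | Contribution to power |
|---|---|---|
| Stop for efficacy | 0.443 | 0.443 |
| Continue to 67 events | 0.211 | 0.204 |
| Increase to 120 events | 0.178 | 0.177 |
| Stop for futility | 0.168 | 0 |
| **Total** | 1.000 | **0.824** |

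If the futility recommendation is overridden and those trials run to 67 events, they add 0.098, giving 0.922.

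**Step 4: the same at true HR 0.55.** Futility stop 37.2%; increase 22.3%. Power is 0.218 + 0.170 + 0.209 = 0.597. Overriding futility, again to 67 events, adds 0.128, giving 0.725. Once the increase is triggered, the chance of rejection is 93.9%, but it is triggered in fewer than a quarter of trials.

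**Step 5: checks.**
- The hazard-ratio cuts are described as approximate. Solving for conditional power of exactly 80% and 50% under the observed effect puts them at 0.541 and 0.616. Power is then 82.7% at HR 0.45 and 59.8% at HR 0.55.
- Two patient-level log-rank simulations (exponential PFS, control median 6 months, 114 patients over 12 months, 50 more over months 12 to 24 if increased, no dropout; 20,000 trials per hazard ratio) gave 81.8% and 81.7% power at HR 0.45, with 17.2% and 17.6% futility stops. One was also run at HR 0.55 and gave 59.5% power.
- The design with the futility rule followed reaches 90% power at a true hazard ratio of about 0.40.
- One-sided type I error is 0.025 with the efficacy looks only, 0.014 with all rules followed, and 0.023 with futility overridden to 67 events.

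**The case against.** The strongest reply is that no stated figure is false. The sentence in 16.1 describes a log-rank test at 67 events, and for that test 90% is right. The sentence about 120 events is explicitly conditional and also right. This stands. The fault is that the Synopsis gives the fixed-test figure as the basis for the size of a trial that will not always reach 67 events.

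A second reply is that the rule looks advisory. The outcomes are recommendations, the cuts are approximate, and the two significance levels spend the full one-sided 0.025 on the efficacy looks, so no alpha is reclaimed from futility stopping. Boundaries set for a non-binding rule look like this, and on the override reading 90% is slightly conservative. The evidence leans that way but does not settle it: fixed cuts are paired with an instruction to terminate, and a charter outside these documents may decide the matter. A non-binding rule also costs power whenever it is followed.

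Third, hazard ratio 0.55 is not the planning alternative, so its overall power answers a question the plan does not pose. That is fair as regards priority. It is worth stating because the plan prints 90% beside 0.55 and a reader may take it as the design's power there.

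**Conclusion.** The point holds. The 90% is the power of a fixed 67-event test, not of the design described in Protocol 16.6 and SAP 8.3. With the rules followed as written, power at hazard ratio 0.45 is about 82%, so the risk of missing the planned effect is 17.6% rather than 10%. The result is stable at 82% to 83% across the written cuts, the exact conditional-power cuts and simulation. It rests on proportional hazards and on the futility recommendation being followed. If it is overridden and those trials run to 67 events, power is about 92%; the documents do not say how far such trials would run. Type I error is lowered, not inflated. The plan should be corrected, but the 67-event calculation, the boundaries and the tests remain valid.

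**What to change.** In the Synopsis, Protocol 16.1 and SAP 7.0, replace the power statements with text to this effect:

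> A log-rank test at 67 events (two-sided 0.0476) has 90% power at HR 0.45, and a log-rank test at 120 events has about 90% power at HR 0.55. With the interim rules applied and the futility recommendation followed, the power of the design is about 82% at HR 0.45 and about 60% at HR 0.55.

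In Protocol 16.6 and SAP 8.3, state whether the futility rule is binding. If it is non-binding, say how many events an overridden trial would run to, and give the power for that case: about 92% at HR 0.45 and 73% at HR 0.55 if it runs to 67 events. The committee charter should say the same.

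The power statement is a wording change; no event count, boundary or test is altered. Declaring the rule's status is a decision for the sponsor and may need a formal amendment under Protocol 11.5. The drawback is a less favourable stated power. Whether to move the futility cut is a separate trade-off and not part of this correction.

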17.0 DOCUMENTATION

A log of all patients evaluated for this protocol must be maintained at each site. Patients excluded from admission will be provided with a clear explanation of the specific reasons why they have been excluded from the study. Patients who are included will be assigned a patient identification number.

For each patient treated with the study drug(s), the Investigator or their designee is required to prepare and maintain case histories that include all observations and other data pertinent to the investigation. This will include all source documents needed to verify the accuracy of all observations and other data contained in the eCRFs on each study patient.

The Investigator or his/her designee is required to retain the records related to the trial for a period of 2 years following the date a marketing application is approved for the indication being investigated. If no application is to be filed or if the application is not approved for such indication, the records must be retained until 2 years after the investigation is discontinued and the regulatory agencies are notified.

The Investigator shall retain study drug disposition records and source documents for the maximum period required by the country and institution in which the study will be conducted, or for the period specified by Gradalis, whichever is longer. The Investigator must contact Gradalis, Inc. prior to destroying any records associated with the study.

If the Investigator withdraws from the study (e.g., relocation, retirement), the records shall be transferred to a mutually agreed upon designee (e.g., another investigator, IRB). Notice of such transfer will be given in writing to Gradalis, Inc.

